### 5.8.2. Index Date and Follow-up

*The date following the last date of the baseline period will be defined as the index date. The end of the study will occur on the last date that administrative claims data will be available, September 30, 2022.*

*For PLWH who receive PCV13 after their index date, we will include the time between their index date and the 13 days after their PCV13 vaccination date as unvaccinated follow-up time. Any outcomes occurring during this time will be counted as events in the unvaccinated*

*cohort. Follow-up that occurs 14 days after PCV13 vaccination will be defined as vaccinated follow-up time.*

*Unvaccinated (no PCV13) PLWH will be followed from their index date until the earliest occurrence of the following: 13 days after PCV13 vaccination, death, end of health plan enrollment, or end of study period. Vaccinated PLWH will be followed from 14 days after their PCV13 vaccination date or index date if they were vaccinated during the baseline period, until the earliest occurrence of the following: death, end of health plan enrollment, or end of study period.*

#### **5.8.3. Minimum Sample Size Requirements**

In order to maintain patient de-identification, outcomes, covariates and subgroups will have at least 10 patients/ events in each category for inclusion in outputs.

#### **5.8.4. Inverse Probability of Treatment Weighting for Time-Varying Exposures**

Except for patients vaccinated more than 13 days before the end of the baseline period, exposure (vaccination) status will not be fixed at start of follow-up, with patients able to receive PCV13 during follow-up. Therefore, PCV13 will be considered a time-varying exposure. The values for some clinical characteristics may also change during the study period and values during baseline may be poor proxies for covariate values at the various points during the follow-up. Therefore, some covariates will be treated as time-varying confounders (Section 5.3.2).

Inverse probability of treatment weighting (IPTW) will be generated from predicted probabilities of vaccination status (propensity scores) to create pseudo-populations where any imbalances in the potential confounders by vaccination status are reduced. For the analyses of first events, stabilized weights will be generated for each patient for the baseline period and every 30 days from index during the follow-up until the earliest of the following: outcome, death, end of health plan enrollment or end of study period. For the analyses of recurrent events, stabilized weights will be generated for each patient for the baseline period and every 30 days from index during the follow-up until the earliest of the following: death, end of health plan enrollment or end of study period. This aims to make vaccination status independent of the measured confounders at each of the follow-up timepoints [9]. The weights will be used to estimate the average treatment effect (ATE). For the analysis of RZV, stabilized weights will be generated every 90 days instead of 30, due to the expected lower numbers of patients vaccinated with RZV overall and in each interval.

The numerators for the stabilized weights will be the estimated probability of a patient's observed vaccination status at timepoint given their prior vaccination status and time-fixed covariates. The denominators will be the estimated probability of a patient's observed vaccination status at the given timepoint given their prior vaccination status, time-fixed covariates and time-varying covariates. Numerators and denominators after vaccination will be set to 1 and the cumulative product of these ratios will be calculated, therefore IPT

weights after vaccination will be constant. Time-varying covariates will be lagged, i.e., within each 30-day (or 90-day for RZV) interval the vaccination status will be the status at the end of the interval, whereas the values for the covariates will be from the end of the previous interval. Cox proportional hazards models will be used to model the associations between vaccination status and the numerators and denominators.

It is possible that censoring may be informative, with patient characteristics associated with loss to follow-up. Therefore, patients who are censored may have different risks of the study outcomes than patients who are not censored. Inverse probability of censoring weighting (IPCW) will also be generated during the follow-up using the above methods for IPTW. These weights will be multiplied by the IPT weights to produce a new set of weights [9].

Distributions of the IPT, IPC and IPT\*IPC weights will be summarized by vaccination status. In the presence of extreme/outlier weights, stabilized weights may be truncated at the 1st and 99th percentiles for use in the Cox models for the outcomes. Although there is no formal definition of an extreme weight, the need for truncation will be judged based on the distributions and the potential effect on the interpretation of results [9].

Weights for first and recurrent events will be generated separately in datasets created for each study outcome; however, all weights will be derived without assessing their impact on the VE estimates. Weights will also be generated again in each of the subgroups. The weights will be generated using the *ipwtn* function within the *ipw* R package [10]. Example R code is provided in Appendix 7.2.

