### 5.5. Treatment Labels

Information on PCV13 vaccination status will continue to be collected on and after index date and will therefore be treated as a time-varying exposure. PLWH in the study will be assigned to 'PCV13 Vaccinated' or 'PCV13 Unvaccinated' according to their vaccination status by each person-time record during the follow-up. Individuals will be considered vaccinated from 14 days after their PCV13 vaccination date till the remainder of their follow-up.

National Drug Codes (NDC) and Current Procedural Terminology® (CPT) codes used to identify PCV13 receipt are listed in Appendix Table 7.3.

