#### **5.8.6. Incidence Rates**

Incidence rates will be reported using first episodes only and again after including recurrent episodes of the same type. Crude incidence rates and 95% CIs will be presented as episodes per 100,000 person-years by PCV13 vaccination status for each outcome overall as well as annually and during time periods of interest (0-3, 3-5 and 5-7 years).

For incidence rates based on first episodes only, the total unvaccinated person-time will be calculated as time from index date to the earliest of the following: outcome, 13 days after their PCV13 vaccination, death, end of health plan enrolment or end of study period. The

total vaccinated person-time will be calculated as time from 14 days after their PCV13 vaccination date or index date, if they were vaccinated more than 13 days before the end of the baseline period, to the earliest of the following: outcome, death, end of health plan enrolment or end of study period.

For incidence rates including recurrent episodes of the same type (separated by at least 90 days), the total unvaccinated person-time will be calculated as time from index date to the earliest of the following: 13 days after their PCV13 vaccination, death, end of health plan enrolment or end of study period. The total vaccinated person-time will be calculated as time from 14 days after their PCV13 vaccination date or index date, if they were vaccinated more than 13 days before the end of the baseline period ,to the earliest of the following: death, end of health plan enrolment or end of study period. Person-time will exclude any time the patient is not at risk, i.e. the first 89 days after an episode. Cluster robust standard errors will be used in the calculation of 95% confidence intervals to account for multiple events per patient.

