#### 5.8.12. Analysis of Negative Control Outcomes and Exposure

The number of patients with the negative control outcome(s) will be presented by PCV13 vaccination status at the time of occurrence. Crude incidence rates and 95% CIs will be presented by PCV13 status for first and recurrent (separated by at least 90 days) episodes. Unadjusted and Cox-MSM will be used to obtain crude and weighted VE estimates and 95% CIs of PCV13 on candidiasis.

The number of patients who receive at least one dose of RZV by the end of the overall follow-up will be reported. Patients will be considered vaccinated with RZV 14 days after their vaccination date. Unadjusted and Cox-MSM will be used to obtain crude and weighted VE estimates and 95% CIs of RZV on each of the study outcomes of interest. Cox-MSM will additionally adjust for the main exposure of PCV13 as a time-varying covariate. Patients who have evidence of RZV before the six-month baseline period will be excluded from the negative control exposure analysis.

Weighted 95% CIs for the VEs that exclude 0% would suggest the presence of residual confounding in the weighted models between PCV13 and the study outcomes. If so, the results for the main outcomes may be corrected for bias identified from the negative control outcome.

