### 7.2. Appendix B: R Example Code

#### 7.2.1. Example Data Formats for First Event and Recurrent Events

Example dataset for time to first outcome:

ptid	tstart	tstop	pcv13	ipd	x1	x2	xt1	xt2	censor	endfu
1001	-1	0	0	0	1	0	0	0	0	87
1001	0	30	0	0	1	0	0	0	0	87
1001	30	60	1	0	1	0	1	0	0	87
1001	60	87	1	0	1	0	1	0	1	87
1002	-1	0	0	0	0	0	0	0	0	45
1002	0	30	0	0	0	0	0	1	0	45
1002	30	45	0	1	0	0	1	1	0	45

Example dataset including any subsequent outcomes:

ptid	tstart	tstop	pcv13	ipd	x1	x2	xt1	xt2	censor	endfu2
1001	-1	0	0	0	1	0	0	0	0	87
1001	0	30	0	0	1	0	0	0	0	87
1001	30	60	1	0	1	0	1	0	0	87
1001	60	87	1	0	1	0	1	0	1	87
1002	-1	0	0	0	0	0	0	0	0	106
1002	0	30	0	0	0	0	0	1	0	106
1002	30	45	0	1	0	0	1	1	0	106
1002	45	60	0	0	0	0	1	1	0	106
1002	60	84	0	1	0	0	1	1	0	106
1002	84	90	0	0	0	0	1	1	0	106
1002	90	106	0	0	0	0	1	1	0	106

Where:

- *ptid*: patient identifier
- *tstart*: first day of interval. -1 represents baseline period
- *tstop*: last day of interval
- *pcv13*: binary indicator for time-varying PCV13 vaccination status (exposure)
- *ipd*: binary indicator for IPD event (outcome)
- *x1, x2, ..., xn*: time-fixed confounders
- *xt1, xt2, ..., xtn*: time-varying confounders
- *censor*: binary indicator for censoring event

- *endfu*: last day of follow-up up to any first event
- *endfu2*: last day of follow-up

For binary variables, 1 indicates Yes, 0 indicates No. Note, all variables in dataset must be numeric for the *ipwtn* function.

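### Appendix 7.2 of the SAP reuses the 30-day weight-model vaccination flag in the rates and outcome Cox models, which credits event-free unvaccinated time to PCV13 and pushes VE upward

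*SAP*

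**What the plan says.** Three parts of the SAP text fix the switch to an exact day:

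- Section 5.5: "Individuals will be considered vaccinated from 14 days after their PCV13 vaccination date till the remainder of their follow-up".
- Section 5.8.2, for doses after index: "we will include the time between their index date and the 13 days after their PCV13 vaccination date as unvaccinated follow-up time". Events in that time count as unvaccinated.
- Section 5.8.6: "vaccinated person-time will be calculated as time from 14 days after their PCV13 vaccination date or index date", the index date applying to those vaccinated more than 13 days before baseline ends.

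Section 5.8.4, on weight construction, works on a 30-day grid (90-day for RZV): "within each 30-day (or 90-day for RZV) interval the vaccination status will be the status at the end of the interval". It exempts from time-varying status only one group: "Except for patients vaccinated more than 13 days before the end of the baseline period".

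The example dataset in 7.2.1 has one `pcv13` column, defined there as the exposure, and `tstop` is the "last day of interval". Rows are cut at events and at the end of follow-up (days 45, 84, 87, 106), but no cut at dose plus 14 days is shown. Section 7.2.2 builds the weights from `pcv13` in `ipdfirst` and binds them back to the same rows. Section 7.2.3 computes rates from whole-row person-time by `pcv13`, and 7.2.5 fits the outcome Cox models on the same rows and flag.

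For the negative controls, section 5.8.12 says: "Weighted 95% CIs for the VEs that exclude 0% would suggest the presence of residual confounding in the weighted models".

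**The concern.** An end-of-interval status is harmless for estimating the probability of vaccination. Used as the exposure in an outcome model, it creates immortal time. Someone who switches on day 55 is coded vaccinated from day 30, and those 25 days are event-free by construction. Someone with an event on day 45 has a row that ends there, with `pcv13` = 0. Time moves to the vaccinated side and events do not. IPTW and IPCW balance covariates and censoring; they cannot correct person-time assigned to the wrong group.

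Three things are at stake: an upward shift in PCV13 VE; a larger shift in the 0-3 year window than later, which can resemble waning; and negative controls that look protective because of coding and would be read as residual confounding. RZV is the most exposed, because its rows are three times as long.

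**Working it through.** **1. Is the flag in `ipdfirst` really the end-of-interval one?** The balance code in 7.2.4 keeps rows starting on day 360 for people whose `pcv13date14` (dose plus 14 days) is later than day 360 or missing, then uses `pcv13` as the treatment. With exact-day coding nobody in that set could have `pcv13` = 1. A treated group exists only if rows starting before the switch already carry 1, and this is the dataset that feeds the Cox models.

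**2. Inputs.** From Protocol 9.5: 175,000 people; 56,000 (32%) vaccinated after the first HIV code; all-cause pneumonia 5,487 and IPD 183 per 100,000; VE 5-15% and 7.5-22.5%; annual censoring 4% or 10%; maximum 97 months. Assumed, because not documented: 35% have the full 97 months and the rest enter uniformly; vaccination rate in follow-up is constant; 0, 10 or 20% of the cohort is vaccinated during baseline, within the 32%.

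**3. Calibration to the plan's own counts** (97 months, none vaccinated in baseline, 4% / 10% censoring). IPD at VE 7.5%: 1,493 / 1,226, against 1,492 / 1,272 in Table 2. All-cause pneumonia at VE 5%: 38,309 / 31,972, against 38,848 / 33,257 in Table 3. The entry pattern was chosen to fit, so this shows plausibility and is not an independent reproduction.

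**4. Formula.** For switch day *s* the coded switch is *g* = 30 × floor(*s*/30), so *s* − *g* days move, about 15 per follow-up vaccinee. With *m* the total time moved, the rates become D_v/(P_v + m) and D_u/(P_u − m). At true VE 0% and 4% censoring, both should be 5,487 per 100,000. With none vaccinated in baseline they become 5,414 and 5,512, so VE = 1 − 5,414/5,512 = 1.8%. With 20% they become 5,463 and 5,497, so VE = 0.6%.

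**5. First-event Cox models, all-cause pneumonia, 97 months** (expected-count solution on a 1-day grid; exact-day coding recovers the true VE). Estimated VE (%) by share vaccinated in baseline:

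| True VE | Censoring | 0% | 10% | 20% |
|---|---|---|---|---|
| 0% | 4% | 2.0 | 1.2 | 0.6 |
| 5% | 4% | 6.9 | 6.2 | 5.6 |
| 15% | 4% | 16.7 | 16.0 | 15.5 |
| 0% | 10% | 2.4 | 1.5 | 0.7 |

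Table 3 gives a CI of 2 to 7 at VE 5%, a half-width of (7 − 2)/2 = 2.5. Shifts of 1.9, 1.2 and 0.6 points are about three quarters, one half and one quarter of it. The shift falls below 1 point once about 13% (4% censoring) or 15% (10% censoring) of the cohort is vaccinated in baseline: 0.13 × 175,000 ≈ 23,000 or 0.15 × 175,000 ≈ 26,000 of the 56,000.

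A separate paired simulation, with a slightly different assumed entry pattern, gave +1.8 points at VE 5% with none vaccinated in baseline, and +1.2 to +2.2 across assumed entry and vaccination timing.

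**6. IPD at VE 7.5%:** shift 0.5 to 1.9 points, against a CI of −5 to 19.

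**7. Time windows, all-cause pneumonia, true VE 0%, 4% censoring.** Estimated VE (%):

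| Vaccinated in baseline | 0-3 y | 3-5 y | 5-7 y |
|---|---|---|---|
| 0% | 3.5 | 1.3 | 1.0 |
| 10% | 1.7 | 1.0 | 0.8 |
| 20% | 0.7 | 0.6 | 0.5 |

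From unrounded values the false decline from the first to the last window is 2.6 / 1.0 / 0.3 points. The standard error of that difference is 3.1 to 3.3.

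**8. Recurrent all-cause pneumonia, true VE 0%:** shift 1.6 / 1.1 / 0.6 points if rows cut at an event take their status at `tstop`. It is about zero if they take the 30-day grid status, but then pre-switch events count as vaccinated, contrary to 5.8.2. The SAP does not say which applies.

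**9. Negative control outcomes.** A null outcome at an assumed 183 to 5,487 per 100,000 per year shows VE of 1.8-2.0 / 1.1-1.2 / 0.5-0.6%. With none vaccinated in baseline the CI is −0.4 to 4.4 at 5,487 (rule not met) and 0.4 to 4.2 at an assumed 10,000 (rule met). If the optional correction is a ratio of HRs (assumed), it would roughly cancel the artefact: 1 − (1 − 0.069)/(1 − 0.020) = 5.0%. Uncorrected VE and the rates would keep it.

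**10. RZV, 90-day rows, about 45 days moved per vaccinee.** The simple ratio 45/(45 + days at risk) gives 45/1,140 = 4% at 3 years, 45/775 = 6% at 2 years and 8% at 1.4 years. The Cox calculation at assumed uptake of 5 / 10 / 15% gives 4.2 / 4.4 / 4.8%, 6.4 / 7.1 / 8.0% and 9.1 / 10.5 / 12.5%. At 3 years the CI is −1.0 to 9.2 with 5% uptake (rule not met) and 0.7 to 8.1 with 10% (rule met).

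All calculations are unweighted. Weighting and robust errors would widen the CIs.

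**The case against.** The governing text is already right: every SAP statement about person-time uses dose plus 14 days, and the end-of-interval sentence sits in the section on weights. Appendix 7.2 is labelled example code and would not run as printed. The weights argument falls outside the `coxph` call, `event`, `patient` and `patid` are not columns of the dataset, and the recurrent example has events 39 days apart although 5.3.1 collapses claims less than 90 days apart. A missing split row is therefore weak evidence about the production program. The 2-point shift needs nobody to be vaccinated in baseline, whereas the design provides for baseline vaccination. The RZV inputs are assumed, the appendix contains no RZV code, and the optional correction draws on the negative control outcome, not on RZV.

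Most of this stands as a limit on size and certainty: the bias is conditional on the code being followed, and the baseline split could bring it well below 1 point. It does not remove the conflict. Nothing in the SAP confines the end-of-interval flag to the weights or calls for a second, exact-day flag, and the balance code needs the end-of-interval version in the same dataset that feeds the Cox models. A programmer following the appendix's logic, with its slips repaired, would breach 5.5, 5.8.2 and 5.8.6.

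**Conclusion.** The concern holds: the appendix contradicts the SAP's own exposure definition. For first events the direction is certain if the code is followed: VE goes up. For all-cause pneumonia the shift is about 0.6 to 2 points at 4% censoring, up to 2.4 at 10%, depending mainly on the undocumented share vaccinated in baseline. At VE 5% it stays inside the planned CI half-width but can use most of it, and a larger sample would not shrink it. For IPD it is minor. Any false waning is below its own standard error. For recurrent events the shift depends on a coding rule the SAP leaves open. The RZV analysis is the most sensitive, and an interval excluding 0% there could come from coding alone, though its size rests on assumed uptake and time at risk. This should be fixed before the outcome models are run; if they have already been run, check how the exposure rows were built.

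**What to change.** - In 5.8.4, state that end-of-interval status is used only to build the weights.
- After the weights are bound to the rows in 7.2.2, split each person's record at dose plus 14 days (`pcv13date14`, and the RZV equivalent). Set exposure to 0 before and 1 after. Use these rows for the incidence rates and for every outcome Cox model: overall, piecewise, recurrent-event and negative control.
- State which weight the pre-split part carries. The previous cumulative weight is the natural choice, since the person is still unvaccinated, but the unweighted calculations here do not test it.
- State that rows cut at an event take the exact-day status.
- Amend the 7.2.1 example to show a split, for instance rows 30-44 with `pcv13` = 0 and 44-60 with `pcv13` = 1.
- Report how many of the 32% were vaccinated during baseline.

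The cost is a few sentences of SAP text, one row-splitting step, one amended example and one reported count. No new data are needed, and the definitions in 5.5, 5.8.2 and 5.8.6 stay as they are.

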### 7.2.2. Code for Generating IPTW and IPCW

```
library(ipw)
iptw <- ipwtn(exposure = pcv13, family = "survival",
numerator = ~ x1 + x2 + ... + xn, denominator = ~ x1 + x2 + ... + xn + xt1 + xt2 + ... + xtn,
id = ptid, tstart = tstart, timevar = tstop, type = "first",
data = ipdfirst)
ipcw <- ipwtn(exposure = censor, family = "survival",
numerator = ~ x1 + x2 + ... + xn, denominator = ~ x1 + x2 + ... + xn + xt1 + xt2 + ... + xtn,
id = patient, tstart = tstart, timevar = tstop, type = "cens",
data = ipdfirst)
iptw.stab<-iptw$ipw.weights
ipcw.stab<-ipcw$ipw.weights
ipdfirst<-cbind(ipdfirst, iptw.stab, ipcw.stab)
ipdfirst$comb.weights<- ipdfirst$iptw.stab*ipdfirst$ipcw.stab

#Plot of stabilized weights during follow-up in unvaccinated
ipwplot(weights = subset(ipdfirst$iptw, ipdfirst$pcv13==0),
subset(timevar = ipdfirst$tstop, ipdfirst$pcv13==0),
binwidth = 183, ylim = c(-1.5, 1.5), main = "Stabilized weights",
xlab = "Years Since Index", ylab = "Logarithm of Stabilized IPTW",
xaxt = "n", yaxt = "n")
axis(side = 1, at = seq(0, 15, 1), labels = as.character(seq(0, 15, 1)*0.5))
axis(side = 2, at = c(-1.5, -1, -0.5, 0, 0.5, 1, 1.5),
labels = as.character(c(-1.5, -1, -0.5, 0, 0.5, 1, 1.5)))
```

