#### 7.2.4. Code for Standardized Differences

```
library(cobalt)
smdDataY1<-subset(ipdfirst[ipdfirst$tstart==360 &
  (ipdfirst$tstart < ipdfirst$pcv13date14 | is.na(ipdfirst$ pcv13date14)),])
#Where pcv13date14 is 14 days after the PCV13 vaccination date
covs <- subset(smdDataY1, select = c(x1, x2, ...))
#Before IPTW
smdsUn<-bal.tab(covs, treat = smdDataY1$pcv13, continuous = "std",
  binary = "std", s.d.denom = "pooled")
x1SmdUn<-smdsUn$Balance[1,2]
x2SmdUn<-smdsUn$Balance[2,2]
...
#After IPTW
smdsWt<-bal.tab(covs, treat = smdDataY1$pcv13, continuous = "std",
```

```
binary = "std", s.d.denom = "pooled", weights=smdDataY1$iptw.stab)
x1SmdWt<-smdsWt$Balance[1,3]
x2SmdWt<-smdsWt$Balance[2,3]
```

```
...
```

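### The treatment-weight model dates PCV13 at dose + 14 days, so for 14 of every 30 follow-up dose dates the lagged covariates are read on the day of the dose or up to 13 days after it

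*SAP*

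**What the plan says.** Four parts of the SAP combine here.

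- **Exposure.** Section 5.5: "Individuals will be considered vaccinated from 14 days after their PCV13 vaccination date till the remainder of their follow-up". Section 5.8.4 carries the same offset into the weighting text. It opens "Except for patients vaccinated more than 13 days before the end of the baseline period" and treats everyone else's status as able to change during follow-up.
- **Grid.** Section 5.8.4: "stabilized weights will be generated for each patient for the baseline period and every 30 days from index during the follow-up". For RZV the step is 90 days.
- **Lag.** Section 5.8.4, on each interval of that grid: "the vaccination status will be the status at the end of the interval, whereas the values for the covariates will be from the end". The covariate day meant there is the last day of the preceding interval.
- **Code.** Section 7.2.2 passes `pcv13` to `ipwtn` as the exposure. Section 7.2.1 defines `pcv13` as the time-varying status and lists no dose-date variable. Section 7.2.5 uses the same variable in the outcome Cox model. The balance check in 7.2.4 decides who is still unvaccinated from `pcv13date14`, with the comment "Where pcv13date14 is 14 days after the PCV13 vaccination date".

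Section 5.8.12 applies a 14-day delay to RZV as well.

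**The concern.** The 14-day delay marks when person-time starts to count as vaccinated. The propensity model has a different task: it should describe who gets vaccinated, and that is settled on the day of the dose. A covariate lag keeps later information out of that model only if it is measured from the dose. Here it is measured from the interval in which the delayed status changes, so the reading day can fall after the dose.

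Several covariates can change at a vaccination visit or shortly after it. Under SAP 5.3.2 an influenza vaccine or annual exam sets a flag for 365 days, CD4 and viral-load tests do the same, and a new hospitalization stays flagged for the rest of follow-up. If such an event falls on the dose day or soon after, whether it enters the vaccination model depends on where the dose lies in a 30-day grid counted from index.

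Because IPT weights are held constant after vaccination (5.8.4), a weight affected in this way applies to all of that person's vaccinated time. The balance check uses the same delayed date, so it is not designed to reveal the problem.

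**Working it through.** The documents give no figure on this point to reproduce. The check follows each possible dose day through the SAP's own rules.

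**Inputs**
- Offset from dose to vaccinated status: 14 days (SAP 5.5; 5.8.12 for RZV).
- Interval length: 30 days from index for PCV13, 90 days for RZV (SAP 5.8.4).
- Covariate reading day: the end of the previous interval, which is the start of the current one (SAP 5.8.4).

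**Formulas**
- Dose on follow-up day D. Switch day F = D + 14.
- F lies in the interval (a, a + 30], and covariates are read on day a.
- The reading is on or after the dose if D ≤ a, and strictly after it if D < a.

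**Worked dose days**

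| Dose day D | Switch F | Interval | Covariates read | Reading relative to dose |
|---|---|---|---|---|
| 17 | 31 | (30, 60] | day 30 | 13 days after |
| 23 | 37 | (30, 60] | day 30 | 7 days after |
| 30 | 44 | (30, 60] | day 30 | same day |
| 31 | 45 | (30, 60] | day 30 | 1 day before |
| 46 | 60 | (30, 60] | day 30 | 16 days before |

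**Count over D = 1 to 2910 (97 intervals of 30 days)**
- On or after the dose: days 17-30 of each interval, 14/30 = 46.7% (1,358 of 2,910).
- Strictly after: 13/30 = 43.3%.
- Before the dose, by 1 to 16 days: 16/30 = 53.3%.
- Left-closed intervals, with covariates from the last day of the previous interval, give the same 46.7%.
- RZV on the 90-day grid: on or after 14/90 = 15.6%; strictly after 13/90 = 14.4%.

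**From dates to doses.** 46.7% is a share of dates. The share of doses needs an assumption on timing, which the documents do not give. With exponential dose times it is 46.6% for a constant hazard reaching 32% over 97 months, 45.6% for a hazard of 1 per year, and 40.5% for an extreme mean time to dose of 60 days.

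**Doses around baseline.** A dose within 13 days of the end of baseline switches on days 1-14 and has covariates read at day 0, so the reading is on or after the dose for all of these. Doses earlier in baseline are already exposed at index and lie outside this point.

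**With the switch dated at the dose (offset 0).** 0 of 30 dose days have covariates read on or after the dose. The reading is always 1 to 30 days before it.

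**The case against.** The strongest counter-argument is that the SAP defines exposure as status from dose + 14, and 5.8.2 counts days 0-13 as unvaccinated time with any events assigned there. The lagged covariates always precede exposure in that sense. They are post-dose, not post-exposure. A reader might infer that the weights adjust for consequences of vaccination. The documents do not support that: if protection has not begun by day 13, a hospitalization in that window is not yet an effect of protection. This part of the objection stands.

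A reader might also infer that nearly half of vaccinees receive a wrong weight. That does not follow either. The 47% says where the reading date falls, not whether any value changes. Many patients in regular care will already be flagged for exam, influenza vaccine or laboratory tests, comorbidity and hospitalization flags stay on once set, and ART adherence updates only every 180 days. Multiplying 47% by the 56,000 recipients in Protocol 9.5 would be wrong for this reason, and because that total includes baseline doses. In first-event analyses, a person who has the analysed outcome on days 0-13 never switches status at all.

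Finally, dating the event at the dose means that same-visit markers of care seeking are never adjusted for, and care seeking is a confounder that SAP 5.8.8 worries about. That cost is real. It does not rescue the present rule, which adjusts for those markers at 14 of 30 dose days and not at the other 16, a split that no view of confounding would produce.

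**Conclusion.** The point holds for doses given during follow-up and for those within 13 days of the end of baseline. The weight model's lag works for 16 of 30 follow-up dose dates. For the other 14 (47%; 13 of 30 strictly after; 14 of 90 for RZV), covariates are read on or up to 13 days after the dose. Same-visit or post-dose influenza vaccine, exam, CD4 or viral-load test, or hospitalization is therefore handled differently by grid position alone.

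This rests on the weight model using the dose + 14 status. Sections 5.5, 5.8.4, 7.2.1, 7.2.2 and 7.2.4 all point that way, and no section says otherwise. If the programmers in fact use the dose date there, the share is zero and the SAP should say so.

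The documents do not allow a count of patients whose weight changes, and they give neither the size nor the direction of any VE bias. This is an inconsistency in the specification that is worth correcting. It is not evidence that the VE estimates are materially wrong.

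**What to change.** 1. In the weight dataset, set the vaccination event in the interval that contains the actual dose date, with time-varying covariates from the end of the interval before it.
2. Use the dose date instead of `pcv13date14` for the SMD risk sets in SAP 7.2.4.
3. In the outcome dataset, keep the 14-day rule of 5.8.2 by splitting rows at dose + 14.
4. State which weight applies between the two dates: days 0-13 are unvaccinated time and carry the patient's last pre-dose weight, and the vaccinated weight applies from dose + 14.
5. Do the same for RZV.

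**Cost.** One date variable and a change of SAP wording. No new data are needed, because the dose date is already required to compute `pcv13date14`. The weight and outcome datasets will have different switch dates and must be merged by patient and day. Same-visit markers of care seeking will consistently go unadjusted, so the dose + 14 version can be kept as a sensitivity analysis to show whether that matters.
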